3.1.3.7 Percent compliance with IP

The percent compliance with study drug will be estimated using dosing information reported in the eDiary as follows:

$$\frac{[\text{number of days with study medication taken} = \text{Yes}]}{(\text{number of days with study medication taken reported})} \times 100$$

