6.2.2. Dosing

Ganaxolone will be administered in increments of 15 mg/kg/day up to 63 mg/kg/day (maximum 1800 mg/day) given as an oral suspension with food. Patients weighing \leq 28 kg will be dosed on an mg/kg basis. Patients weighing $>$ 28 kg will be dosed on a fixed regimen in increments of 450 mg/day up to 1800 mg/day. All IP prescribed per day will be administered in 3 divided doses following a meal or snack. Ganaxolone is to be administered during the 4-week titration period as follows:

Table 3: Oral Suspension Dosing^a for Patients Weighing \leq 28 kg (62 lbs)^b

Dose mg/kg	Total mg/kg/day	Days
6 TID	18	1-7
11 TID	33	8-14
16 TID	48	15-21
21 TID	63	22-28

TID = three times daily

a. To be administered in 3 divided doses following a meal or snack.

b. Patients weighing \leq 28 kg will be dosed according to the patient's weight in kilograms.**Table 4: Oral Suspension Dosing^a for Patients Weighing $>$ 28 kg (62 lbs)^b**

Dose mg	ml per Dose	Total mg/day	Days
150 TID	3	450	1-7
300 TID	6	900	8-14
450 TID	9	1350	15-21
600 TID	12	1800	22-28

TID = three times daily

a. To be administered in 3 divided doses following a meal or snack.

b. Patients weighing $>$ 28 kg will be dosed on a fixed regimen in increments of 450 mg/day up to 1800 mg/day.

Any patient not tolerating the next dose step can be maintained at the lower dose step for additional days before advancing to the next dose. If the next dose is still not tolerated, the patient can drop back to the next lower dose step. A minimum dose of 33 mg/kg/day or 900 mg/day is generally required following the escalation period, during the maintenance period.

Dose changes including alternative dosing paradigms (e.g., lower dose during the daytime and higher dose in the evening) should be discussed with the sponsor medical monitor prior to making the change or within 48 hours of making the change. However, the final decision to adjust drug dosages lies with the investigator. For any patient who is unable to be maintained at the minimum dose, the investigator should contact the sponsor medical monitor to discuss continued IP dosing. Patients who discontinue GNX treatment before the completion of the maintenance period in Part A will continue to be followed per protocol and, at a minimum, patients will be encouraged to maintain daily seizure diary entries until Part A is completed.

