6.2.3. Dose Administration

Investigational product will be provided as an oral suspension. **Ganaxolone must be taken with a meal or snack.** Note: grapefruit and grapefruit juice, Seville oranges and star fruit are prohibited during the study.

Ganaxolone oral suspension will be administered through an oral dosing syringe administered by parents/caregivers TID, following the morning, noon, and evening meal or snack. Each dose should be separated by a minimum of 4 hours and a maximum of 12 hours. A missed dose of IP may be taken up to 4 hours before the next scheduled dose; otherwise, the missed dose should not be given.

Prior to each dose, the following instructions should be followed:

1. Manually shake bottle end to end, 2-3 times per second, for 1 minute
2. Allow the bottle to stand for 1 minute
3. Attach the dosing apparatus (adaptor with syringe), invert the bottle and remove the indicated dose
4. Administer dose as indicated

Please use a new dosing syringe and adapter every day. Dosing syringes should be cleaned with hot water rinse and air-drying between first, second, and third daily doses.

Patients and their parent or legal guardian will be informed about possible side effects from the IP and cautioned to avoid quick postural changes, at least until they know how the IP affects them. Patients will be advised that the IP might affect mental alertness. They will also be cautioned that non-adherence to the dosing instructions (e.g., increasing the dose, taking the IP doses too close together) could produce side effects.

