6.4. Investigational Product Accountability

Investigators will be provided with sufficient amounts of the IP to carry out this protocol for the agreed number of patients. The investigator or designee will acknowledge receipt of the IP, documenting shipment content and condition. Accurate records of all IP dispensed, used, returned, and/or destroyed must be maintained as detailed further in this section.

The investigator has overall responsibility for administering/dispensing IP. Where permissible, tasks may be delegated to a qualified designee (e.g., a pharmacist) who is adequately trained in the protocol and who works under the direct supervision of the investigator. This delegation must be documented in the applicable study delegation of authority form.

The investigator or their designee (as documented by the investigator in the applicable study delegation of authority form) will administer and/or dispense the IP only to patients included in this study following the procedures set out in the study protocol. Each patient will be given only the IP carrying his or her treatment assignment. All administered and/or dispensed IP will be documented on the eCRFs and/or other IP record. The investigator is responsible for ensuring the retrieval of all IP and study supplies from patient.

The patient's parent/caregiver must be instructed to save and bring their unused IP and empty/used IP packaging to the clinic and final follow-up visit or to ship it back to the site via secure courier. Investigational product accountability must be assessed at the container/packaging level for unused IP that is contained within the original tamper-evident sealed container (e.g., bottles) or at the individual count level for opened containers/packaging. The pharmacist/nominated person will record details on the IP accountability form.

No IP stock or returned inventory from a Marinus-sponsored study may be removed from the site where originally shipped without prior knowledge and consent by the sponsor. If such transfer is authorized by the sponsor, all applicable local, state, and national laws must be adhered to for the transfer.

The sponsor or its representatives must be permitted access to review the supplies storage and distribution procedures and records.

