2.2 ANALYSIS SETS

Analysis sets for this study are defined as:

- Screened population: all patients who have signed informed consent for the study.
- Safety population: all patients who have received at least one dose of GNX
- Intent-to-treat (ITT) population: all patients who receive at least one dose of GNX and have at least one post-baseline efficacy assessment.
- Per-protocol (PP) population: includes all ITT patients without major protocol violations, as will be defined prior to database lock. Patients that fall below 80% compliance at two consecutive visits during the maintenance period (i.e. Visits 4 and 5, Weeks 5 and 12) will not be included in the PP population.
- Open-label extension (OLE) population: includes all ITT patients who participate in the OLE (Part B) of the study and receive at least one dose of GNX in the Part B.
- Pharmacokinetic (PK) population: all ITT patients who have had at least one PK sample collected and a valid bioanalytical result obtained. Pharmacokinetic data collected from this population may be reported separately.

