4.1.6 Treatment Compliance

Compliance with GNX treatment will be assessed by inspecting the seizure and medication diary entries and returned drug supply with queries as necessary. Treatment compliance will be calculated as explained in Section 3.1.3.7. Percent compliance for Parts A and B of the study will be summarized for the Safety Population and OLE Population, respectively. Reported dosing by visit and calculated compliance values will be listed.

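### Compliance is a daily yes/no ratio for a drug given three times a day, with Yes undefined, so the 80% per-protocol rule does not track doses taken

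*SAP*

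**What the plan says.** SAP 3.1.3.7 introduces its formula with "The percent compliance with study drug will be estimated using dosing information reported in the eDiary as follows". The numerator is the "number of days with study medication taken" with the answer Yes, and the denominator is the "number of days with study medication taken reported". Both are counts of days. Neither document defines Yes or reproduces the wording of the diary item.

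The drug is not given once a day. Protocol 6.2.2 states "All IP prescribed per day will be administered in 3 divided doses following a meal or snack", and Protocol 6.2.3 has the suspension "administered by parents/caregivers TID, following the morning, noon, and evening meal or snack".

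The ratio feeds a rule. In SAP 2.2, "Patients that fall below 80% compliance at two consecutive visits during the maintenance period" are left out of the per-protocol (PP) set, the visits being 4 and 5. Patients with major protocol violations are also left out; these are to be defined before database lock. SAP 4.2.1.2 repeats the primary analysis in the PP set and lists no other sensitivity analysis.

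SAP 4.1.6 says that compliance is assessed from diary entries and "returned drug supply with queries as necessary" (Protocol 6.5 is similar), but it refers the calculation to 3.1.3.7 alone. Protocol 6.4 requires accountability of unused drug by container if sealed, and "at the individual count level for opened containers/packaging".

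**The concern.** With three scheduled doses a day, adherence on any day can be 0, 1/3, 2/3 or 1. A yes/no item keeps only one cut across that scale, and the SAP does not say where the cut lies. The 80% threshold is then applied to a quantity that can sit far from the share of doses taken. This is separate from the treatment of blank diary days. It remains when every day is answered.

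Partial days are foreseeable. Under Protocol 6.2.4 a dose missed too close to the next one is not made up, and the caregiver is told to call the site only after two or more consecutive missed days. Protocol 8.1.7 does not treat missed doses as reportable medication errors. The compliance figure is therefore where isolated missed doses would be expected to appear.

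At stake are which patients enter the PP repeat of the primary analysis and what the compliance tables for Parts A and B tell a reader about drug intake.

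**Working it through.** The documents give no worked compliance value to reproduce; the only stated number is the 80% cut-off.

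**Inputs.** Doses per day: 3 (Protocol 6.2.2). Maintenance: 8 weeks = 56 days (Protocol 3.2), so 56 × 3 = 168 scheduled doses. The diary is taken as complete, so all 56 days are reported. The two meanings of Yes are assumptions, since the SAP gives none.

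**Formulas.** SAP compliance = Yes-days / reported days × 100. Dose-level compliance = doses taken / doses scheduled × 100.

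| Doses taken each day | SAP value, Yes = any dose | SAP value, Yes = all doses | Dose-level value |
|---|---|---|---|
| 1 of 3 | 56/56 = 100% | 0/56 = 0% | 56/168 = 33.3% |
| 2 of 3 | 56/56 = 100% | 0/56 = 0% | 112/168 = 66.7% |
| 3 of 3 | 100% | 100% | 168/168 = 100% |

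**At the cut-off.**
- Yes = any dose: Yes on 80% of days with one dose on each gives 0.80 × 1/3 = 26.7% of doses, and the patient is not below 80%.
- Yes = all doses: 79% of days complete and 21% with two of three doses gives 79 + 21 × 2/3 = 93.0% of doses, and the patient is below 80%.
- In whole days of 56, the nearest cases are 45 days (80.4%) with 45/168 = 26.8% of doses, and 44 days (78.6%) with (132 + 24)/168 = 92.9% of doses.

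**Could returned supply show the gap?** Take a patient over 28 kg on the 12 mL three-times-daily step throughout maintenance (Protocol Table 4), with 110 mL bottles (Protocol 6.1). Expected use is 12 × 3 × 56 = 2016 mL, or 18.3 bottles. One dose in three uses 672 mL, or 6.1 bottles. The difference is 1344 mL, about 12 bottles. That is large enough to prompt a query, but no rule turns it into the compliance percentage.

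**What a volume denominator must respect.** On the Table 4 schedule, a patient who takes every dose uses 9, 18, 27 and 36 mL/day over the four titration weeks: 7 × 90 = 630 mL. Week 5 adds 7 × 36 = 252 mL, for 882 mL by Visit 4. A flat 36 mL/day over 35 days would be 1260 mL, and 882/1260 = 70%. A fully adherent patient would then fall below 80% at Visit 4, so the denominator has to follow the doses actually prescribed.

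**The case against.** A reader might infer that the formula counts any day with a dose as compliant, and so overstates drug intake. The documents do not support that. Yes is undefined, and under the all-doses meaning the error runs the other way. The any-dose meaning is a natural sense of a daily item, but it remains an assumption.

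A reader might also infer that a patient taking one dose in three stays in the PP set. That does not follow either. The set also excludes major protocol violations, and the list is still open. One third of 1800 mg/day is 600 mg/day, below the 900 mg/day that Protocol 6.2.2 describes as generally required in maintenance, so such a patient could be classed as a violator. Protocol 6.4 requires supply discrepancies to be investigated, and both documents provide for queries on returned drug. These safeguards are real. But nothing lists under-dosing as a major violation, and nothing says that a supply discrepancy changes the percentage. What can be said is that, under the any-dose meaning, the 80% rule itself does not remove this patient.

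Intake is also reported elsewhere. SAP 4.3.1 summarises total dosage received and lists total daily dose, and SAP 4.1.6 lists reported dosing by visit. Neither section says that every missed dose is captured, and neither feeds the PP rule.

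Finally, the consequence is limited. The study is descriptive with about 30 patients, and the ITT analysis keeps all available seizure data whether or not treatment was stopped. That stands, and it limits the severity.

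**Conclusion.** The concern holds in this form: a day-level yes/no ratio with an undefined Yes cannot support an 80% threshold for a drug given three times daily. The same complete diary at two of three doses daily scores 100% or 0%, depending on an unwritten convention, against a dose-level 66.7%. At the threshold, the share of doses taken can be as low as 26.7% in a patient who passes (any dose) or as high as 93.0% in a patient who scores 79% (all doses). These are bounds from constructed patterns, not expected values. Exclusion also requires a score below 80% at both Visits 4 and 5.

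The effect is confined to the PP sensitivity analysis and the compliance summaries. The change should be made before database lock, but the primary result does not depend on it.

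**What to change.** In SAP 3.1.3.7:

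1. Define what a Yes day means.
2. If the eDiary records each dose, set compliance = doses taken / doses prescribed × 100.
3. If it does not, set compliance = (amount dispensed − amount returned) / amount prescribed over the interval × 100. Take the numerator from the accountability records and the denominator from the patient's recorded daily doses, including titration steps and dose changes.
4. Apply that figure to the 80% rule at Visits 4 and 5, and state the interval each visit covers. Table 1 schedules dispensing at Visits 2, 4 and 5, which gives natural intervals.
5. Use the diary day ratio only as a named fallback when returned amounts are missing, and report how many patients rely on it.

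The cost is a SAP edit and a new derivation. Families are already told to bring back all bottles at the next visit (Protocol Appendix 3), and Protocol 6.4 has returned drug counted or measured. That does not guarantee a volume in mL for every opened bottle, so some returns will be missing or approximate. The denominator also needs patient-level dose histories; SAP 4.3.1 already plans to list daily dose with start and end dates.

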3.2 ANALYSIS VISIT WINDOWS

Efficacy Analyses

Efficacy analyses will use data only from scheduled visits. Data will be reported by designated visit.

Data collected at unscheduled visits will be provided in listings.

For analysis of data collected across specific study periods, the following definitions will be applied:

- Baseline period: Visit 1 to Visit 2; Study Week -4 (Day -32 ± 4) through Study Day 0 (date of first dose of IP)
- Titration period: Visit 2 + 1 day to Visit 4; Study Day 1 through Study Week 4 (Day 28 ± 3 days; date of Visit 4)
- Maintenance period: Visits 4 + 1 day and 5; Study Week 5 (± 3 days) through Study Week 12 (± 3 days)
- 12-week treatment period: titration period + maintenance period (including taper and safety visits if not continuing in OLE)
- OLE period if continuing in OLE: Visit 5 + 1 day through final visit

Safety Analyses

Safety data will be summarized by actual visit. No visit windowing will be applied.

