3.4. Discussion of Study Design

Dosing will be based on doses that have been shown to be safe in children and adults in multiple studies with normal volunteers and individuals with epilepsy. In this current study, patients will receive OL GNX, prescribed in increments of 15 mg/kg/day up to 63 mg/kg/day given as an oral suspension with food, during a 4-week titration period, 8-week maintenance period, and optional extension period. Patients weighing ≤ 28 kg will be dosed on an mg/kg basis. Patients weighing > 28 kg will be dosed on a fixed regimen in increments of 450 mg/day up to 1800 mg/day.

Ganaxolone will be administered during the 4-week titration period as follows:

1. For patients weighing \leq 28 kg (62 lbs):

- 6 mg/kg three times daily (TID) (18 mg/kg/day) suspension - Days 1-7
- 11 mg/kg TID (33 mg/kg/day) suspension - Days 8-14
- 16 mg/kg TID (48 mg/kg/day) suspension - Days 15-21
- 21 mg/kg TID (63 mg/kg/day) suspension - Days 22-28

2. For patients weighing $>$ 28 kg (62 lbs):

- 150 mg TID (450 mg/day) suspension - Days 1-7
- 300 mg TID (900 mg/day) suspension - Days 8-14
- 450 mg TID (1350 mg/day) suspension - Days 15-21
- 600 mg TID (1800 mg/day) suspension - Days 22-28

Any patient not tolerating the next dose step can be maintained at the lower dose step for additional days before advancing to the next dose. If the next dose is still not tolerated, the patient can drop back to the next lower dose step. A minimum dose of 33 mg/kg/day or 900 mg/day is generally required following the escalation period and during the maintenance period.

Patients will initiate treatment in Part B with GNX at the same dose they were on at the completion of the maintenance period. During the extension period, doses of GNX may be adjusted to a maximum of 600 mg TID for patients weighing $>$ 28 kg and a maximum dose of 21 mg/kg TID for patients \leq 28 kg.

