7.2.2. Baseline (Visit 2, Week 0 + 4 days)

The 4 weeks between the Screening Visit and the Baseline Visit can be no less than 28 days and no more than 32 days. The following study procedures/assessments are to be completed prior to IP administration:

- Review of inclusion/exclusion criteria
- Medical history review
- Review genetic testing results for patients that were screened without previous genetic testing results and had a genetic test performed at the sponsor's designated lab
- SIF/DRF (Epilepsy Study Consortium) approval
- Vital signs (to include BP, HR, RR, and body temperature)

- Weight
- Physical, neurological, and developmental examination (developmental examination is limited to pediatric patients 2 to 17 years of age, inclusive)
- ECG
- Clinical laboratory tests (chemistry and hematology)
- Urinalysis (If the urine sample was not collected at screening, it must be collected at baseline)
- Drug screen (plasma) for THC and CBD
- Serum pregnancy test for all girls/women of childbearing potential
- Concomitant AED review and levels if per standard of care
- AEs
- Seizure and medication diary review
- [REDACTED]
- CGI-C (parent/caregiver/LAR identified behavioral target). During the baseline visit, the investigator and parent/caregiver/LAR will decide on a domain and identify the specific behavior that the patient exhibits that denotes the domain. This behavior will be used at subsequent visits to assess change after the initiation of IP.
- CGI-I (parent/caregiver/LAR and clinician)
- Columbia-Suicide Severity Rating Scale (C-SSRS) (baseline form) for patients \geq 7 years old if appropriate. Otherwise clinical judgment will be used.
- Dispense IP

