7.2.5. Titration Period (Phone Follow-ups, Weeks 2, 3, and 4 ± 3 days)

A telephone follow-up visit will be conducted at Weeks 2, 3, and 4 (\pm 3 days) to assess the following:

- AEs
- Seizure and medication diary review

7.2.6. Maintenance Period (Visits 4 and 5, Weeks 5 and 12 ± 3 days)

The following study procedures/assessments will be completed at Weeks 5 and 12 (\pm 3 days):

- Vital signs (to include BP, HR, RR, and body temperature)
- Weight
- Physical, neurological, and developmental examination (developmental examination is limited to pediatric patients 2 to 17 years of age, inclusive)
- ECG
- Clinical laboratory tests (chemistry and hematology)
- Urinalysis
- Drug screen (plasma) for THC and CBD (Visit 5 [Week 12])
- Serum pregnancy test for all girls/women of childbearing potential
- IP PK sample (Visit 4 [Week 5], between 1-5 hours after last IP dose and Visit 5 [Week 12], between 4-8 hours after last IP dose)
- Concomitant AED review and levels if per standard of care
- [REDACTED]
- AEs
- Seizure and medication diary review
- [REDACTED]
- CGI-C (parent/caregiver/LAR identified behavioral target)
- CGI-I (parent/caregiver/LAR and clinician)
- C-SSRS (since previous visit). Only for patients \geq 7 years old if appropriate, otherwise clinical judgement will be used.

- Dispense IP

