4.2 EFFICACY ANALYSES

4.2.1 Primary Efficacy Analysis

4.2.1.1 Primary Analysis

The primary efficacy endpoints, the percent change in 28-day primary seizure type frequency through the end of the 12-week treatment period (Part A; 4-week titration and 8-week maintenance) relative to the baseline, is defined in Section 1.2.1. The calculation of the primary endpoint is described in Section 3.1.3.

Descriptive summaries including the number of patients with non-missing primary seizure data, mean arithmetic change and percent change in 28-day primary seizure type frequency from baseline and associated 95% confidence intervals, SD, minimum, median and maximum values will be presented for the baseline period, 4-week titration period, 8-week maintenance period and 12-week treatment period. All patients in the ITT population and all available seizure data within Part A of the study will be included in these analyses regardless of whether the patient stopped taking IP or took rescue medication.

Additionally, a by-patient listing of seizure data collected during Part A will be provided.

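### SAP 3.2 gives two incompatible boundaries between titration and maintenance (Day 28 and the date of Visit 4); if Visit 4 is programmed, about a week of maintenance is reported as titration.

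*SAP*

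**What the plan says.** SAP 3.2 lists period definitions to be applied to efficacy data collected across study periods. Titration is "Visit 2 + 1 day to Visit 4; Study Day 1 through Study Week 4 (Day 28 ± 3 days; date of Visit 4". The next bullet reads "Maintenance period: Visits 4 + 1 day and 5; Study Week 5 (± 3 days) through Study Week 12 (± 3 days". Both bullets name Visit 4 as the dividing point, and the first dates it to Day 28 ± 3.

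Other parts of the documents place Visit 4 a week later:

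- Protocol 7.2.6 is headed "Maintenance Period (Visits 4 and 5, Weeks 5 and 12 ± 3 days".
- SAP 2.2, on compliance for the per-protocol set, refers to two visits "during the maintenance period (i.e. Visits 4 and 5, Weeks 5 and 12".
- Protocol Table 1 and its copy in SAP Appendix A show Visit 4 in the Week 5 column, ± 3 days.
- The Week 4 contact is a telephone call: Protocol 7.2.5 is headed "Titration Period (Phone Follow-ups, Weeks 2, 3, and 4 ± 3 days".

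The last scheduled titration step in Protocol 3.4 is "21 mg/kg TID (63 mg/kg/day) suspension - Days 22-28".

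The split feeds reported results. SAP 3.1.3.2 calculates a separate maintenance-period frequency. SAP 4.2.1.1 says that summaries, with 95% confidence intervals for the changes, "will be presented for the baseline period, 4-week titration period, 8-week maintenance period and 12-week treatment period".

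**The concern.** A programmer cannot follow both halves of the titration definition for a patient seen on schedule. One half (Day 28) gives the period lengths that the SAP states. The other half (the Visit 4 date) moves the first maintenance week into titration. The resulting tables would still be labelled 4-week and 8-week.

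Two things are at stake. First, the titration summary could mix titration days with days after the scheduled end of titration. Second, a visit-based boundary has no value when the visit did not happen. A patient whose diary ends between Day 28 and Visit 4 has observed maintenance days, but no maintenance period to put them in. SAP 3.3 says that available data from patients who withdraw early will be included.

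The study is open-label, so a choice between two readings that is left to the programming stage may be made with the data in view.

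**Working it through.** **Inputs**

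- Visit 2 is Week 0: "Baseline (Visit 2, Week 0 + 4 days" (Protocol 7.2.2). Week k is therefore Day 7k, counting Visit 2 as Day 0.
- Visit 4 is Week 5 ± 3 days: Day 35, range 32-38. Visit 5 is Week 12 ± 3 days: Day 84, range 81-87.
- SAP 3.2 dates Visit 4 as Day 28 ± 3: Days 25-31.
- Stated lengths (SAP 3.1.3.2): 4 weeks = 28 days, 8 weeks = 56 days, total 84 days.

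**Formulas:** titration days = Visit 4 day; maintenance days = Visit 5 day − Visit 4 day; maintenance days counted as titration = Visit 4 day − 28.

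| Boundary day | Visit 5 day | Titration | Maintenance | Maintenance days counted as titration |
|---|---|---|---|---|
| 28 (the SAP's day) | 84 | 28 | 56 | 0 |
| 35 (Visit 4 on schedule) | 84 | 35 | 49 | 7 |
| 32 (earliest Visit 4) | 87 | 32 | 55 | 4 |
| 38 (latest Visit 4) | 81 | 38 | 43 | 10 |

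The stated 28 + 56 is reproduced only with the boundary on Day 28. With Visit 4 inside its scheduled window, maintenance runs from 43 to 55 days and does not reach 56. On schedule it loses 7/56 = 12.5% of its planned days. The windows 25-31 and 32-38 do not overlap.

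**Can another convention rescue the text?** Reading Week k as the first day of the k-th week puts Week 5 at Day 29. It also puts Week 1 at Day 1 and Week 12 at Day 78, which conflicts with Visit 2 as Week 0 and with Week 12 closing a 12-week period. SAP 3.1.2 makes the first-dose day Day 1, where SAP 3.2 makes it Day 0. That moves labels by one day, not seven.

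**Effect on the summaries** (assumed percent changes, complete diaries, constant rate within each planned period; split at Day 35)

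Reported titration change = (28 × titration change + 7 × maintenance change)/35.

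- −10% then −30%: (−280 − 210)/35 = −14%, instead of −10%.
- −10% then −50%: (−280 − 350)/35 = −18%, instead of −10%.
- −30% throughout: −30%, no shift.

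The maintenance figure is unchanged in each case (−30%, −50%, −30%). The 12-week figure is (28 × titration change + 56 × maintenance change)/84 = −23.3%, −36.7% and −30%, wherever the inner boundary falls.

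**The case against.** The strongest reply is that the definition also contains the right answer. Its Day 28 half, with Study Week 5 through Study Week 12 in the next bullet, gives the 4 + 8 weeks named elsewhere. A sensible programmer might use it, and SAP section 7 defers detailed specifications to a separate document that could settle the matter. This stands to the extent that nobody can say the maintenance result will cover seven weeks. It does not remove the conflict, because Visit 4 is the boundary named in both bullets. Nor is the conflict a matter of protocol versions: the SAP's own section 2.2 and Appendix A put Visit 4 at Week 5.

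A reader might infer more than the documents support:

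- *That the maintenance estimate is biased.* Frequency is seizures per day with diary data, times 28, so a shorter window does not itself shift the rate. The days from Visit 4 + 1 to Visit 5 all lie after the scheduled end of titration.
- *That a titration-versus-maintenance comparison is distorted.* None is planned; each period is compared with baseline.
- *That patients who stop drug in Week 5 vanish from maintenance.* Protocol 3.1, 3.2 and 4.5.1 provide for diaries to continue to the end of maintenance, and Table 1 note n encourages attendance at all scheduled visits. SAP 4.2.1.1 uses all Part A seizure data regardless of stopping. The loss concerns only patients whose diary ends after Day 28 and before Visit 4, at most about 10 diary days each. The documents give no basis for the number of such patients.
- *That the main endpoints are affected.* The primary and ≥50% responder endpoints both use the full 12 weeks.

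All analyses are also descriptive, which limits the consequence.

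**Conclusion.** The contradiction is real and lies within the SAP as well as between the SAP and the protocol. It supports two different splits. Under the Visit 4 reading, about 7 days (4-10) of planned maintenance are reported as titration, and maintenance loses about one eighth of its days. These sizes assume visits within their windows and a program that uses the Visit 4 date.

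The substantive error under that reading is in the titration summary, by an amount that depends on how far the effect differs between the periods and is zero if it does not. For maintenance the cost is a wrong label, some precision, and the few patients described above. The point deserves correction because both summaries are prespecified efficacy results. It does not touch the primary or responder result.

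**What to change.** In SAP 3.2, remove the reference to the Visit 4 date and the ± 3 days from the boundary, and split by calendar day from first dose. For example:

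- Titration: date of first dose + 1 day through date of first dose + 28 days (28 days).
- Maintenance: date of first dose + 29 days through the date of Visit 5, or through the last diary day up to the end of Week 12 if Visit 5 did not occur. This is 56 days on schedule, and 53-59 with Visit 5 at ± 3 days.

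Apply this to every patient with diary days in the interval, whether or not Visit 4 took place. State the day convention, since SAP 3.1.2 and SAP 3.2 number the first-dose day differently. Protocol 6.2.2 allows a patient to stay longer at a dose step, so also state that the analysis split is by calendar day even where an individual's titration was prolonged.

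The cost is one SAP definition and the matching program line. No new data are needed, and the conduct of the study does not change.
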